9.3.2 Administration of Medication

The Registry is an observational study and for this reason no treatment will be administered per protocol requirement. Information concerning administration of medication will be collected from the practice of the routine clinical care. Details of weekly Lamzede therapy and concomitant therapies received by the patient either in hospital or in home infusion settings, where allowed per local practice, will be collected at baseline and within the overall duration of the study. Setting of treatment administration will be collected as well.

9.3.3 Assessments

For the baseline visit and each follow-up routine clinical visit the following information will be reported in the eCRF if considered necessary and available as part of routine clinical practice by the treating physician:

- Genetic mutations testing, residual enzymatic activity (at Baseline only).
- Anti-velmanase alfa-IgG antibody (ADA) test in serum*. Only for patients receiving Lamzede treatment, at Baseline for patients about to start Lamzede therapy. Additional measurements will follow the judgment of the treating physicians.
- Laboratory chemistry and standard haematological if available per clinical practice:
 - Hemoglobin, hematocrit, platelet count, red blood cells, white blood cells with differential count (band forms, segment forms, neutrophils, eosinophils, basophils, monocytes, lymphocytes) (all expressed in % as well as in absolute numbers). Blood smear for leukocytes detection by electronic microscopy may be done at the treating physician's discretion.
 - Biochemistry: Serum electrolytes (sodium, potassium, calcium, inorganic phosphate), creatinine, creatine-kinase, amylase, AST, ALT, ALP, albumin, bilirubin (total and direct), LDH.
- Oligosaccharides in serum*
- 3MSCT (annually, see Section 9.3.3.3 for further details of the 3MSCT), when applicable.
- 6MWT (annually, see Section 9.3.3.3 for further details of the 6MWT), when applicable.
- 2MWT (annually, see Section 9.3.3.3 for further details of the 6MWT), when applicable
- FVC, as litre and as percentage of predicted, annually, when applicable.
- Serum IgG and IgA*
- Serum IgM.
- Electrocardiogram (ECG) (annually; more frequently in treatment-naive patients if considered necessary by the treating physician).
- Hearing test (by pure tone audiometry [PTA]) (annually).
- Occurrence of infections, antibiotic treatment requirement and length of treatment.
- Occurrence of psychotic events.
- Occurrence of all AEs/ADRs based on all risk categories associated with Lamzede EU RMP, including non-serious and Serious AEs, ADRs, AEs leading to treatment discontinuation and AEs leading to death at any time they become available.

Functional tests included in the Global Treatment Response (GTR) (namely 3MSCT, 6MWT, EQ-5D-5L and FVC are considered not doable in very young paediatric patients (i.e. < 4 years), due to the subject's inability to adequately execute the tests. Therefore, pre-treatment data will not be collected in this population (limited to these tests) in the infrequent case of patients starting treatment

Clinical Protocol Number: CLI-LMZYMAA1-12

Clinical Protocol Version Number: 8.0	Date: 01 February 2019

before 4 years Concerning the 2MWT will be eventually performed according to the judgment of the treating physician For non-treated patients who are enrolled at such young age, but start treatment later, it will be strongly advised to the treating physician to take care of the fact that at least one pre-treatment battery of motor function tests is performed.

*Serum oligosaccharides, serum IgG, IgM and IgA, anti-velmanase alfa-IgG antibody (ADA) will be assessed by a centralised and specialised laboratory. In Germany these markers will not be evaluated by the central laboratory, but theywill be evaluated for German patients only locally in accordance to German requirements as part of routine clinical practice.

This centralised evaluation is needed to perform the quantitative detection by validated and consistent methods of the mentioned biochemical parameters, as specialised laboratories in these specific determination might be not locally available yet or some variability among different laboratories might introduce at certain extent limits in results' comparability. The MAH reassures that patients will not be undergoing additional or other than routine testing based on inclusion into the registry and that the testing within the Registry will only take place as part of routine clinical practice.

On the other hand, the MAH is not in the position, as per current rules, to offer the collection of serum samples for the testing of serum oligosaccharides, IgG, IgM and IgA and ADA as part of general clinical practice to patients treated with velmanase alfa who are not willing to participate in the registry and who are not signing the relevant informed consent form prior to any study related procedures and data collection.

The MAH acknowledges that according to German local rules and specific requirement the above markers will not be evaluated by the central laboratory for German patients only, so that markers testing will take place locally in Germany as part of routine clinical practice.

9.3.3.1 Serum oligosaccharides

Oligosaccharides can be detected quantitatively by a validated liquid chromatography-tandem mass spectrometry (LC-MS/MS)) analyses of serum. The oligosaccharide content in serum of subjects before and after ERT is used as an important biomarker to assess the efficacy of Lamzede in alphamannosidosis subjects. The assessment is recommended as per If further medicinal products will be applied besides Lamzede® for the treatment of alpha mannosidosis all medicinal products have to be administered in accordance with their respective SmPCs and in line with usual clinical practice.

Table 1.

9.3.3.2 Development of Antibodies to velmanase alfa (ADA) Antibody Testing

Serum samples for anti-velmanase alfa antibody (ADA) testing will be obtained as per If further medicinal products will be applied besides Lamzede® for the treatment of alpha mannosidosis all medicinal products have to be administered in accordance with their respective SmPCs and in line with usual clinical practice.

Table 1.

9.3.3.3 Endurance: 3-Minute Stair Climb Test (3MSCT), 6-Minute Walk Test (6MWT) and 2-Minute Walk Test

The 3MSCT and 6MWT will be administered by a certified physiotherapist when applicable according to the judgment of the treating physician.

The 2MWT will be administered in paediatric subjects below 4 years of age, or when applicable according to the judgment of the treating physician.

In all cases, the investigator will enter data into the eCRF. Each battery of 3MSCT, 6MWT and 2MWT will include two assessments on different days. The best value will be evaluated for effectiveness. A time frame of maximum 3 weeks is applicable for test repetition.

Clinical Protocol Number: CLI-LMZYMAA1-12	
Clinical Protocol Version Number: 8.0	Date: 01 February 2019

The 3MSCT measures limiting factors between multiple systems such as the musculoskeletal, neurological and cardiovascular systems. Stair climbing also provides a functional measure that is commonly performed in daily life and relates to level of the independence and community participation. Skeletal abnormalities and myopathy are common disease manifestations in alpha-mannosidosis and the stair climbing test is associated with measures of lower limb strength and power. Stair climbing also requires a greater range of motion from the joints of the lower limbs and greater strength than level walking [3]; [4]. The test measures the number of steps climbed up in 3 minutes and it will be performed in accordance with the test guidelines.

The 6MWT is a frequently-used indicator of functional exercise capacity. The test measures the distance that a patient can walk on a flat, hard surface in a period of 6 minutes. It evaluates the global and integrated responses of all the systems involved during exercise, including the pulmonary and cardiovascular systems, systemic circulation, peripheral circulation, blood, neuromuscular units and muscle metabolism. The test will be performed in accordance with the American Thoracic Society standards [5].

The 2MWT measures sub-maximal cardiovascular endurance by recording the distance that the participant is able to walk in 2 minutes and is considered a pragmatic alternative for the 'gold standard' 6MWT. This shorter test has been validated for the assessment of exercise capacity and is sensitive to detect response in patients with moderate-severe COPD, interventions in lower limb amputations, the elderly, neuromuscular diseases and chronic heart diseases [6]; [7].

9.3.3.4 Health Assessment Questionnaires

The Quality of Life questionnaires are not mandated by the Registry. For the baseline visit and each annual follow-up routine clinical visit the results from the following health assessment questionnaires will be reported, if available, in the eCRF:

- EQ-5D-5L.
- Zarit Burden Interview.
- CHAQ.
- Behavior Checklists: CBCL prescholar (1.5-5) and scholar (6-18); Adult Behavior Checklist (19-59)/ASR, Older Adult Behavior Checklist (60-and above).

Euro Quality of Life-5 Dimensions (EQ-5D-5L)

The EQ-5D-5L is a validated and standardised measure of health status developed by the EuroQol Group to provide a simple generic measure of health status for clinical and economic evaluation (http://www.euroqol.org/). EQ-5D-5L is filled in by patients; from a cognitive point of view it is easy, since it only takes few minutes to complete the questionnaire. The EQ-5D-5L essentially consists of 2 pages - the EQ-5D descriptive system and the EQ visual analogue scale (EQ VAS). The descriptive system comprises the following 5 dimensions: mobility, self-care, usual activities, pain/discomfort and anxiety/depression. The EQ VAS records the respondent's self-rated health on a vertical VAS where the endpoints are labelled "best imaginable health state" and "worst imaginable health state" (http://www.euroqol.org/). The VAS responses can be used as a quantitative measure of health as judged by the individual patients. The questionnaire will be provided in the country main language. Being self-administered, patients able to tick in the boxes and to indicate their self-rated health on the VAS will fill in the questionnaire.

Zarit Burden Interview

Clinical Protocol Number: CLI-LMZYMAA1-12	
Clinical Protocol Version Number: 8.0	Date: 01 February 2019

The Zarit Burden Interview was developed to measure subjective burden among caregivers. Items were generated based on clinical experience with caregivers and prior studies resulting in a 22-item self-report inventory that examines burden associated with functional/behavioural impairments and the home care situation. The items are worded subjectively, focusing on the affective response of the caregiver.

Scoring/Interpretation: each question is scored on a 5 point Likert scale ranging from 'never' to 'nearly always present'. Total scores range from 0 (low burden) to 88 (high burden).

Childhood Health Assessment Questionnaire (CHAQ)

The custodial parent(s) of all patients will be asked to complete the CHAQ. From the CHAQ the following topics are displayed: dressing and personal care, getting up, eating, walking, hygiene, reach, grip, activities, pain (from VAS), and general evaluation (from VAS).

The score for each question in the CHAQ is based on the following validated scoring system: without any difficulty (0), with some difficulty (1), with much difficulty (2), unable to do (3). For each category, the 2-5 items within the category is averaged for the summary tabulation. Even though this questionnaire is meant for children, the expected low equivalent age of the patients in this study makes the entire study population suitable for the questionnaire. Disability Index, VAS general and VAS pain will be evaluated.

Behavior Checklists and self-administered forms

The Child Behavior Checklist (CBCL) is a parent-report questionnaire on which the child is rated on various behavioural and emotional problems [9]. The preschool forms and profiles span ages $1\frac{1}{2}$ -5 years. The forms are completed by the parent/caretaker who spends the most time with the child on problem items plus descriptions of problems, disabilities, what concerns respondents most about the child, and the best things about the child

The school forms and profiles span ages 6-18 years and is completed by the parents or surrogates, and covers like the pre scholar form various behavioural and emotional problems.

The Adult forms (ABCL completed by a partner or surrogates) and ASR (for self-reporting) include normed scales for adaptive functioning, personal strengths, empirically based syndromes, substance use, internalizing, externalizing, and total problems. In addition, the ASR and ABCL profiles feature DSM-oriented scales consisting of items that experts from many cultures identified as being very consistent with DSM-5 categories.

The Older Adult forms/OASR (self-reported) allow assessments in a variety of contexts, including psychiatric and psychological evaluations; medical care; assessments following significant life changes, such as loss of a loved one or a move to an assisted living environment; and evaluations before and after planned changes and interventions.

9.3.3.5 Serum IgG, IgA, IgM and rate of infections

Serum samples for IgG, IgA, IgM testing will be obtained as per Table 1. Occurrence of infections, length of the episode, antibiotics requirements will be also traced according to Table 1. IgM information will be collected if available in clinical practice as per local laboratory.

Clinical Protocol Number: CLI-LMZYMAA1-12	
Clinical Protocol Version Number: 8.0	Date: 01 February 2019

9.3.3.6 Rate of psychotic events

Anecdotic reductions of the number of psychosis have been reported by the treating physicians. The observation is considered attributable to the general improvement of the physical conditions following treatment with velmanase alfa, while physical changes (i.e. increased pain, somatic complains, unfavourable physical events, physical trauma) might trigger psychotic events to occur or recur. Occurrence and rate of psychotic events will be therefore monitored as per Table 1.

9.3.3.7 Pure Tone Audiometry

A pure tone audiometry (PTA) will be administered to all subjects as per Table 1. PTA will be performed without hearing aids and will be carried out using audiometer earphones in a sound-proof room. Air-conduction and bone conduction will be measured.

9.4 Data Sources

Data sources will include patient medical records and any other records of clinical findings or observations collected as part of routine clinical practice. Retrospective data collection for any relevant measurement present in the patient's clinical records prior to the inclusion in the study will be allowed. The source data will be collected by the investigator in the patient file and captured in the eCRF.

In case a patient is transferred to another continuing care site during the 15-year observational period, the new treating site will be formally involved in the Registry study following a request of authorization submitted to the relevant Ethics Committee and Regulatory Authority to complete the 15-year observational period following the patient and collecting all information as per study protocol.

9.5 Study Size

All patients with alpha-mannosidosis who is willing to participate will be included in the Registry. The size of the registry study is not based on the power to demonstrate a formal statistical hypothesis. However, some scenarios are presented in the table below, considering different proportions of GTR in naïve patients able to perform the functional tests after 3 years of treatment. The proportion of responders, the corresponding expected 95% confidence interval and the confidence width are shown below, assuming at least 70 treated patients will be enrolled.

In this case, it is expected that an exact (Clopper-Pearson) two-sided 95% confidence interval (CI) might be provided with a width ranging from 0.239 (worst case) to 0.199 (best case) assuming GTR of 0.60 or more. Of note, in all scenarios the lower limit of 95% CI is always greater than 45% which is considered a clinical relevant result.

Expected Proportion	95% CI Lower Limit	95% CI Upper Limit	95% CI Actual width
0.60	0.476	0.715	0.239
0.65	0.527	0.760	0.234
0.70	0.579	0.804	0.225
0.75	0.632	0.846	0.214
0.80	0.687	0.886	0.199

Clinical Protocol Number: CLI-LMZYMAA1-12

9.6 Data Management

An eCRF will be filled-in by the investigator and/or his/her representative designee.

Front-end edit checks will run at the time of data collection and back-end edit checks will be used by the Data Manager to check for discrepancies and to ensure consistency and completeness of the data. Questionnaires will be collected on paper and data will be entered in the database by the allocated Contract Research Organisation (CRO).

Medical history, AEs and concomitant procedures will be coded using the Medical Dictionary for Regulatory Activities (MedDRA) dictionary; medications will be coded using the World Health Organization Drug dictionary and Anatomical Therapeutic Chemical classification.

The dictionary version to be use will be the most current version at the time the data collection starts. Considering the long duration of the study, the versions could be updated during the trial by re-coding all terms already entered in database according to the new dictionary version. Re-coded terms will be reviewed by Chiesi for approval.

The detailed process and the coding tools will be specified in the Data Management Plan once the CRO will be selected.

External data (i.e. laboratory data) will be processed centrally^a and results will be sent electronically to the designated CRO.

Access to electronic systems used for data collection will be granted to the study personnel only after appropriate training.

The data checks will be created by a CRO according to its own relevant SOPs. The CRO will be request to produce a Data Validation Plan (DVP). This document is envisaged to describe all online data validation checks and the manual checks, which will be programmed for data cleaning proposal. The DVP online checks will be executed directly after the data entry procedure by saving a single eCRF page. Queries resulting from this process will be automatically posted into the eCRF on an ongoing basis.

The DVP will also detail both consistency and medical checks which will be performed by a CRO personnel (Data Manager, Medical Monitor), leveraging listings generated in SAS based on data extracted from the eCRF. The source data will be collected by the on-site personnel, then transcripted in the eCRF.

The eCRF access will be managed by the CRO, according to its own relevant SOPs.

The access to eCRF will be granted to the CRO, Chiesi and On-site personnel after appropriated training is attended.

Each user will receive a personal account and specific privileges based on the role, and will be able to reset his/her own password in the system.

On-site personnel account will be linked to a single site, enabling to access only the data of the patients enrolled at that specific site; on the contrary, the CRO and Chiesi personnel will be entitled to see all sites data in read-only mode.

The CRO personnel will have also the possibility to issue and manage queries in the system.

An appropriate documentation will be prepared to describe the user account creation and management, roles and corresponding privileges, and training on eCRF system as soon as the CRO will be appointed for the study set-up and conduction.

Clinical Protocol Number: CLI-LMZYMAA1-12	
Clinical Protocol Version Number: 8.0	Date: 01 February 2019

The CRA appointed by the CRO will be in charge to reconciliate any potential discrepancy between data collected in the source document and data reported in the eCRF. In case of discrepancies intercepted during the source data verification or other monitoring activities, the CRA will create a query in the eCRF to be sent to the investigator at the site. The investigator is expected to review each query and evaluate the best option to handle it.

Questionnaires will be managed through a paper process only. Two copies are foreseen to be available: the original form will be shipped to the CRO for entering the data in the study database and the second copy will be archived in the Investigator's Site File at the site. The original copy will then be collected in the main Trial Master.

After the completion of data collection and cleaning, a review meeting will be held to determine the occurrence of any protocol violation and to define the patient populations for the analysis. Once the database has been declared to be complete and accurate, it will be locked, and the planned statistical analysis will be performed.

If the database is unlocked after the initial lock, the process must be carefully controlled and documented; updates to the study data must be authorised by Chiesi.

At the study conclusion, a complete copy of the study data will be created for archival purposes at Chiesi. The investigators will receive copies of the patient data for retention at the investigational sites.

^a Local laboratory will be used in Germany as per local clinical practice. Central laboratory will be adopted in extra-German sites.

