Data Sources: Study Size:	 Vital signs: systolic (SBP) and diastolic blood pressure(DBP), pulse rate (PR) Electrocardiogram (ECG) Laboratory tests (haematology and chemistry) Physical Examination Other Variables In addition the following other variables will be presented: Height, weight, Body Mass Index (BMI) and rate of growth Hearing test (Pure Tone Audiometry) Concomitant procedures and medications Data sources will include patient medical records and any other records of clinical findings or observations collected as part of routine clinical practice. Retrospective data collection for any relevant measurement present in the patient's clinical records prior to the inclusion in the study will be allowed. The source data will be collected by the investigator in the patient file and captured in the electronic Case Report Form (eCRF). All patients with alpha-mannosidosis who are willing to participate will be included in the Registry. The size of the registry study is not based on the power to demonstrate a formal statistical hypothesis. However, some scenarios are presented in the table below, considering different proportions of GTR in naïve patients able to perform the functional tests after 3 years of treatment. The proportion of responders, the corresponding expected 95% confidence interval and the confidence width are shown below, assuming that at least 70 treated patients will be enrolled. In this case, it is expected that an exact (Clopper-Pearson) two-sided 95% confidence interval (CI) might be provided with a width ranging from 0.239 (worst case) to 0.199 (best case) assuming GTR of 0.60 or more. Of note, in all scenarios the lower limit of 95% CI is always greater than 45% which is considered a clinical relevant result. 					
	Broate	Expected Proportion	95% CI Lower Limit	95% CI Upper Limit	95% CI Actual width	
		0.60	0.476	0.715	0.239	
		0.65	0.527	0.760	0.234	
		0.70	0.579	0.804	0.225	
		0.75	0.632	0.846	0.214	
		0.80	0.687	0.886	0.199	
Data Analysis:	Categorical variables will be described by means of absolute and relative frequencies, while continuous variables by means of mean, standard deviation, quartiles, min and max.					

Clinical Protocol Number: CLI-LMZYMAA1-12

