9.2 Setting

9.2.1 Subject Recruitment

The eligible patient population for this Registry includes any patient in the EU suffering from alpha-mannosidosis who is willing to participate, and who meets the inclusion criteria (see below) for this Registry. The recruitment period will be indefinite.

About 30 patients are foreseen as coming from previous Lamzede clinical trials. Each patient will be followed-up for 15 years.

Based on the current unmet medical need, patients can start Lamzede treatment independently from the Registry set up.

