At the time of planning this registry, adopted MCID are: oligosaccharides below 4 umol/L, increase of 7 steps/minute for 3MSCT (proxy: MPS IV A), increase of 30 meters for 6MWT (proxy: Pompe disease), increase of 10% for FVC (proxy: Pompe disease), decrease of 0.13 for CHAQ DI (proxy: Juvenile Arthritis) and of 8.2% for CHAQ pain (as in paediatric rheumatology). However, taking into account the length of this registry and the disease characteristics, if new scientific factors (i.e. knowledge about alpha-mannosidosis, clinical guidance) emerge the criteria used to establish the GTR may be reviewed and additional criteria may be added (like, but not limited to, EQ-5D-5L and serum IgG). The Global Treatment Response rate after 3 years of Lamzede treatment in naïve patients able to perform the functional tests will be evaluated. The proportion of responders and the corresponding exact (Clopper-Pearson) two-sided 95% confidence interval (CI) will be presented.

Effects of baseline characteristics will be evaluated by means of regression/logistic models including:

- age subgroup (<18 years, \geq 18 years),
- gender (male, female),
- genotype by subcellular localization of the protein (Genotype Group 1, Genotype Group 2, Genotype Group 3, as defined by Borgwardt et all., 2015)
- baseline residual enzymatic activity (<10 nmol/h/mg, 10 to <15 nmol/h/mg, \geq 15 nmol/h/mg)
- baseline CHAQ Disability Index (0|-|1, 1-|2, 2-|3)

as covariates.

Clinical Protocol Number: CLI-LMZYMAA1-12	
Clinical Protocol Version Number: 8.0	Date: 01 February 2019

Comparison with control group will be done descriptively, provided that a minimum number of nontreated patients with adequate data will be enrolled. If data will allow, Global Treatment Response after 3 year will be analysed comparing the two groups using propensity score (PS) analysis. The PS will be calculated as the predicted probability of Lamzede-treated vs non-treated patients from a logistic regression. This score represents the "propensity" for an observation to be in a treatment group or the other. The logistic regression model will include the following confounding factors as explanatory variables:

- age subgroup (<18 years, \geq 18 years),
- gender (male, female),
- genotype by subcellular localization of the protein (Genotype Group 1, Genotype Group 2, Genotype Group 3, as defined by Borgwardt et all., 2015)
- baseline residual enzymatic activity (<10 nmol/h/mg, 10 to <15 nmol/h/mg, \geq 15 nmol/h/mg)

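### The precision table counts all 70 treated enrolments as evaluable for the 3-year response rate, with no deduction, so its widths and its 45% statement hold only under an unstated assumption

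*Protocol*

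**What the plan says.** Section 9.5 introduces its scenarios as "considering different proportions of GTR in naïve patients able to perform the functional tests after 3 years of treatment". The only number behind them is "assuming at least 70 treated patients will be enrolled"; the abstract repeats it ("assuming that at least 70 treated patients will be enrolled"). Five rows follow, for response rates from 0.60 to 0.80, with interval widths from 0.239 down to 0.199, and then the sentence that "in all scenarios the lower limit of 95% CI is always greater than 45% which is considered a clinical relevant result".

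Section 9.7.4 defines the quantity in the same way: "The Global Treatment Response rate after 3 years of Lamzede treatment in naïve patients able to perform the functional tests will be evaluated", reported with an exact interval.

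Other sections bear on who can enter that denominator:

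- Section 9.2.1: "About 30 patients are foreseen as coming from previous Lamzede clinical trials". Section 7.1 describes the trial patients as having on-treatment data for up to 48 months.
- Section 9.3.3 treats the functional tests as not feasible below age 4. It says pre-treatment values of those tests will not be collected in patients who start before that age.
- Table 1, footnote 7, makes every assessment conditional on routine practice.
- Section 9.7.7 does not replace missing values.
- Sections 9.1 and 9.2.4 let patients stop Lamzede or leave the Registry at any time.

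**The concern.** The response rate is estimated in a subset: naïve at treatment start, able to do the tests, and assessed after 3 years of Lamzede. The table is sized by a wider group, all treated enrolments. The two numbers agree only if every treated enrolment is naïve, can be tested and is evaluable at 3 years. Section 9.5 does not state that assumption, and other sections make it unlikely.

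The table is the only quantitative justification of study size for the primary effectiveness measure, and it carries a statement about clinical relevance. A reader will take the widths and the 45% floor as what 70 treated enrolments deliver.

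**Working it through.** **Inputs.** n = 70, rates 0.60 to 0.80, two-sided 95% Clopper-Pearson limits and the 45% bar come from section 9.5. About 30 ex-trial patients comes from section 9.2.1. The documents give no 3-year loss rate, so any further loss below is an assumption.

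**Formula.** With x = n × p responders:

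- lower limit = Beta⁻¹(0.025; x, n − x + 1)
- upper limit = Beta⁻¹(0.975; x + 1, n − x)

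**Step 1: reproduce the table.** With n = 70 and x left fractional where needed (45.5 at 0.65, 52.5 at 0.75), all five rows match to three decimals. Whole-number x moves the 0.65 and 0.75 rows by at most 0.008. A Wald interval does not match (0.485 to 0.715 at 0.60). The arithmetic is therefore right, and the full 70 is the denominator, with nothing deducted.

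**Step 2: vary the evaluable number.** Limits, with width in brackets:

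| Rate | n = 70 (stated) | n = 60 | n = 50 | n = 40 | n = 30 |
|---|---|---|---|---|---|
| 0.60 | 0.476–0.715 (0.239) | 0.465–0.724 (0.259) | 0.452–0.736 (0.284) | 0.433–0.751 (0.318) | 0.406–0.773 (0.367) |
| 0.65 | 0.527–0.760 (0.234) | 0.516–0.769 (0.253) | 0.502–0.779 (0.277) | 0.483–0.794 (0.311) | 0.455–0.814 (0.359) |
| 0.70 | 0.579–0.804 (0.225) | 0.568–0.812 (0.244) | 0.554–0.821 (0.267) | 0.535–0.834 (0.300) | 0.506–0.853 (0.347) |
| 0.75 | 0.632–0.846 (0.214) | 0.621–0.853 (0.231) | 0.607–0.862 (0.254) | 0.588–0.873 (0.285) | 0.559–0.889 (0.330) |
| 0.80 | 0.687–0.886 (0.199) | 0.677–0.892 (0.215) | 0.663–0.900 (0.237) | 0.644–0.909 (0.266) | 0.614–0.923 (0.309) |

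**Step 3: ex-trial patients inside the 70 and not naïve.** 70 − 30 = 40, before any other loss. Widths grow by about a third (0.318 / 0.239 = 1.33; 0.266 / 0.199 = 1.34). The lower limit at 0.60 is 0.433, which is 0.017 below the bar. The other four rows stay above it. If a further 10%, 20% or 30% of the 40 are not evaluable (assumed), n is 36, 32 or 28, and the lower limit at 0.60 is 0.424, 0.412 or 0.399. At n = 28 the 0.65 row also falls below the bar, at 0.448.

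**Step 4: ex-trial patients do count.** Only the other losses apply. The 0.60 lower limit stays above 0.45 down to n = 49 with fractional x (70 − 49 = 21 patients lost, or 30%), and down to n = 50 with whole counts. The 0.65 row needs n of at least 29. The rows from 0.70 upward stay above 0.45 even at n = 20. The widths have no such margin: at n = 60 they are already 0.259 to 0.215.

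**The case against.** The strongest defence has five parts.

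1. **The table is correct at n = 70, and the 45% sentence is true of its five rows** (lowest limit 0.476). This stands: there is no calculation error, and the fault is in what 70 denotes.

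2. **Nothing says the roughly 30 ex-trial patients are within the 70.** A reader might infer that the protocol itself fixes the denominator at 40. It does not. The 70 could be read as patients of the kind described in the preceding sentence, and naïve is not defined. Section 9.7.1 sets baseline at the start of Lamzede even when that precedes Registry entry, and section 9.4 allows retrospective data. An ex-trial patient who was naïve when treatment began might therefore contribute a baseline and a 3-year value. This stands too, and makes n = 40 conditional.

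3. **The other losses are unquantified and may be modest.** Section 9.3.3 calls a start before age 4 infrequent. Section 9.7.4 needs only one endpoint in each of two domains, and section 9.7.2 takes the nearest available evaluation, so missing components need not remove a patient. This limits the size of the loss. It does not justify a loss of zero.

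4. **Seventy is a floor and enrolment is open-ended.** True, but the table is presented as what that floor delivers.

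5. **No hypothesis is tested, and the response rates in section 7.1 (79% at 12 months, 88% at last observation) are well above 0.60.** This lowers the practical weight of the one failing row and bears on severity. It does not rescue a sentence that covers every scenario, or the widths.

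**Conclusion.** The point holds in a conditional form. The stated precision belongs to 70 evaluable naïve patients, while the text assumes only 70 treated enrolments.

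- **Widths.** They are too narrow for any evaluable number below 70, however ex-trial patients are counted.
- **The 45% statement.** It fails only if 48 or fewer patients are evaluable (49 with whole counts), and at first only in the 0.60 row. If ex-trial patients are within the 70 and not naïve, that row fails. If they count, the statement survives a loss of up to about 30%.

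A reader might also infer that recruitment must rise to at least 100 treated patients (70 + 30). The documents do not support that: the Registry takes every willing patient, and section 9.5 says its size does not rest on power for a formal hypothesis.

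This should be fixed, but it is not critical. No decision rule depends on the 45% figure, and the final interval will reflect the number actually observed.

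**What to change.** In section 9.5 and in the Study Size part of the abstract:

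1. Tabulate limits and widths by number of evaluable naïve patients, for example 30, 40, 50 and 70, as in the table above.
2. State whether ex-trial patients are within the 70, and whether they count as naïve through a retrospective baseline at the start of Lamzede.
3. Give the expected evaluable number at 3 years, with the assumed loss shown as a range and labelled as an assumption.
4. Limit the 45% sentence to about 50 or more evaluable patients, or delete it.

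The cost is wording and a recomputed table in two places. The stated precision becomes less favourable. No extra patients, visits or procedures are needed.
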